stimulation cycle, the fresh oocytes and all thawed oocytes will be fertilized by ICSI. The freeze-all strategy will be applied in both arms, and single blastocyst frozen embryo transfer will be performed in the next menstrual cycle.

The ongoing pregnancy rate of patients in IVFTA HCM was 45.0% in the Antagonist IVF stimulation group. To show or refute that hypothesis: no significant difference in ongoing pregnancy rates when using DPOS protocol (40 - 42%), we need 657 patients to produce a two-sided 95% confidence interval for the difference in population proportions with a width that is equal to 5% (margin = 5.0%, alpha = 5.0% and power = 80%). Considering a 10% loss to follow-up and protocol violation, we plan to recruit 730 participants (365 per arm). The primary endpoint is the ongoing pregnancy rate after the first completed transfer. Secondary endpoints are ovarian stimulation, embryo culture characteristics, drop-out rate, and DPOS and GnRH antagonist protocol safety.

All analyses will be performed on an intention-to-treat basis using the R statistical package

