### Screening and Enrollment

- **Visit 2** (Day 1: the first day of OS cycle - Ovarian stimulation (OS) starts on the 2nd – 4th of mense):
  - The patients undergo a transvaginal ultrasound to access Antral Follicle Count, ovaries and uterus.
  - Laboratory tests (blood tests, urine test and ECG) will be taken for pre-anesthesia examination; in addition, the hormone values include FSH (follicle-stimulating hormone) – only for the first OS cycle, E2 (Estradiol), LH (luteinizing hormone), P4 (Progesterone) and AMH if the result is not

available within 6 months. A pre-anesthesia examination will ensure the patient is eligible for the oocyte retrieval procedure.

- Screening for eligibility will be performed by treating physicians.
- Eligible participants will be invited to a full discussion with investigators about the Study and given the informed consent form. Patients will be given a period (3-4 hours) during anesthesia testing to understand the information and decide whether they agree to participate in the Study. The investigators will obtain written informed consent from all couples before enrolment. To maximize retention in the trial, a consultation will be available to couples to ensure they understand the procedures well and to address any questions or complaints that arise during the Study.

**Treatment period:** The patient will be treated with an oocyte accumulation strategy, and estimated ovarian stimulation cycles range from two to four cycles to collect at least  $7 \pm 1$  oocytes.

*For the first ovarian stimulation cycle:*

- **Visit 2** (Day 1: the first day of OS cycle - Ovarian stimulation (OS) starts on the 2nd – 4th of mense): After informed consent is obtained, the patient will be indicated randomly with one of the following regimens:

**Group I:** oral DYG (Duphaston) 10mg t.i.d from the first day of OS to the day of final oocyte maturation

**Group II:** GnRH antagonist (Ganirelix 0.25 mg) will be initiated on the fifth day of OS to the day of final oocyte maturation

- **Visit 3** (1st cycle - Day 5 of OS): Transvaginal ultrasound and blood sampling (for hormone check-up) will be performed.
- **Visit 4** (1st cycle - Day 8 of OS): Transvaginal ultrasound and blood sampling (for hormone check-up) will be performed.
- **Visit 5** (1st cycle - Day  $10 \pm 2$  of OS): Transvaginal ultrasound and blood sampling (for hormone check-up) will be performed. A final oocyte maturation injection will be performed.

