## 7.2. Screening and Enrollment

The patients will be checked for inclusion criteria on the second - fourth menstrual day (Visit 2). Laboratory tests (blood tests, urine test and ECG) will be taken for pre-anesthesia examination; in addition, the hormone values include FSH (follicle-stimulating hormone) – only for the first OS cycle, E2 (Estradiol), LH (Luteinizing hormone), P4 (Progesterone) and AMH if the result is not available within 6 months. A pre-anesthesia examination will be performed to ensure that the patient is eligible for the oocyte retrieval procedure.

On the day (Visit 2), screening for eligibility will be performed by treating physicians. If the patients are eligible, we will invite them to a full discussion about the Study and give the informed consent form. We will inform verbal and written consent and explain the relevant information such as study context, objectives, and data collection procedure. Patients will be given a period (3-4 hours) during anesthesia testing to understand the information and decide whether they agree to participate in the Study. The investigators will obtain written informed consent from all couples before enrolment. To maximize retention in the trial, a consultation will be available to couples to ensure they understand the procedures well and to address any questions or complaints that arise during the Study.

When there is an eligible participant to be enrolled in the Study, clinicians from the specific site will enter the study data management center to get the allocation of patients according to a computer-generated randomization list in a 1:1 ratio, with a variable block size of 2, 4, 6 or 8. After randomization, if a participant wishes to change her assigned protocol in the first cycle, she will be considered a crossover but analysed in the group she was assigned (intention-to-treat). However, if she wishes to change the assigned protocol from the second ovarian stimulation cycle or transfer more than one embryo after randomization, it will be considered a protocol violation and excluded from the analysis. Due to the type of interventions, this Study will be label-opened to clinicians who perform ovarian stimulation, oocyte retrieval, and embryo transfer.

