#### *7.3.2. Oocyte retrieval and cryopreservation*

After 36 hours of final maturation injection (**Visit 7**), all follicles greater than 12mm in diameter will be aspirated. In the low ovarian reserve group, oocyte cryopreservation will be applied to collect at least  $7 \pm 1$  oocytes. The patient will be stimulated with the previous OS protocol for the following ovarian stimulation cycle. The visits of the patient will be repeated as the first OS cycle.

Oocytes will be received after 36 hours post-hCG. Then, the cumulus-oocyte complexes (COCs) will be cultured for 2 hours in a CXCM medium (Irvine, USA) (37oC, CO2 6%, O2 5%). After 2 hours, the oocytes will be denuded, and the presence of the first polar body will assess oocyte maturity.

Matured oocytes will be frozen by vitrification (CRYOTEC® Method) (39). Firstly, the oocytes will be balanced in an equilibration solution (ES). When the shape of the oocyte fully recovers, it will be transferred to a Vitrification Solution (VS) with a minimum equilibrium (the limit time is 15 min). The oocyte will be exposed to a vitrification solution by maintaining the same mixture of cryoprotectants but double-concentrated for 50 – 60 seconds. Loading takes place within the next 10 seconds by placing oocytes on the device contained in the minimum volume—immediately plunging into liquid nitrogen-induced vitrification. Three oocytes maximum will be loaded per device container. Oocytes were stored in liquid nitrogen tanks for a variable storage time.

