### **12.3. Statistical analyses**

Statistical analysis will be conducted according to the ITT principle, in which all randomized women will be conducted for the comparison of primary outcomes between treatment groups. The per-protocol analysis may be conducted, but these results would be considered reference only. All tests will be two-tailed, and differences with p-value < 0.05 will be considered statistically significant. The statistical software used was R, version 4.0.5 (R Foundation for Statistical Computing). We will develop a detailed statistical analysis plan that will be completed before data-lock.

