#### *12.3.4. Missing data and sensitivity analysis*

Missing values regarding baseline characteristics, we will first perform an analysis by excluding missing values; we will then perform multiple imputations to impute missing values and conduct subsequent analysis to estimate the robustness of the findings. For the loss of follow-up and protocol violation, we will attempt sensitive analyses to explore the effect of these factors on the trial findings.

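### Section 7.2 drops late regimen switchers and women wanting multiple-embryo transfer from the analysis, while Sections 12.3 and 2.1 analyse everyone by intention-to-treat

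*Protocol*

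**What the plan says.** Protocol Section 7.2 gives two rules for departures from the allocated treatment.

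- A woman who wishes to change regimen in the first cycle stays in: "she will be considered a crossover but analysed in the group she was assigned (intention-to-treat".
- The next sentence opens with the word However. It covers a woman who wishes to change from the second stimulation cycle or to "transfer more than one embryo after randomization, it will be considered a protocol violation and excluded from the analysis".

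The other statements about the analysis population are:

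- Section 12.3 sets an intention-to-treat comparison "in which all randomized women will be conducted for the comparison of primary outcomes between treatment groups".
- Section 12.3 also says: "The per-protocol analysis may be conducted, but these results would be considered reference only".
- Section 2.1 says: "All analyses will be performed on an intention-to-treat basis using the R statistical package".
- Section 12.3.4 treats violations as a sensitivity question: "For the loss of follow-up and protocol violation, we will attempt sensitive analyses".

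**The concern.** A woman cannot be both left out of the analysis and counted among all randomized women compared on the primary outcome. Whoever writes the analysis plan inherits both rules.

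Both triggers arise after randomization, in an open-label trial, and are worded as the woman's wish. The arms differ in ways that could affect that wish: one regimen is oral and the other injected, the introduction (Section 3) suggests the progestin regimen might be more user-friendly and cheaper, and Section 13.2 mentions medication fees for the dydrogesterone group only. If exclusion differs by arm or is related to prognosis, the groups compared are no longer those that were randomized.

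The direction cannot be predicted. Late switchers may have a poorer prognosis. A woman who could have more than one embryo transferred must have at least two, which suggests a better one. Section 8 counts cycles with no blastocyst for transfer as failures; excluding late switchers could take some of those failures back out of the denominator.

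**Working it through.** **Reading the passages together**

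1. In Section 7.2 the exclusion follows directly on an explicit intention-to-treat rule and is set against it by However. It refers to the analysis without qualification and does not mention a per-protocol set. A cycle-1 crossover would normally leave a per-protocol set too, so a per-protocol-only reading removes the contrast the sentence draws.
2. Sections 12.3, 2.1 and 12.3.4 all fit keeping these women in the main analysis. The Section 7.2 clause is the outlier.
3. The triggers are limited but not ruled out. Later cycles repeat the regimen (Section 7.3.2: "The patient will be stimulated with the previous OS protocol for the following ovarian stimulation cycle"), single transfer is an inclusion criterion (Section 6.1), and one embryo is thawed (Section 7.3.5). However, Section 5 expects that "estimated ovarian stimulation cycles range from two to four cycles", so most women should reach the point where the switching rule starts, and Section 7.2 provides for both events.

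**The plan's own figure**

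Section 12.1 inflates 657 by 10% for loss to follow-up and protocol violation combined: 657 / (1 - 0.10) = 730. This reproduces. The allowance is 730 - 657 = 73 women for all causes. No separate rate is given for the two Section 7.2 triggers.

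**Illustration of the possible bias**

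From the protocol: 365 women per arm, a 45% ongoing pregnancy rate (the Section 12.1 control rate) and a two-sided 5% test. Assumed: the true rate is 45% in both arms, a fraction f of an arm is excluded, and the rate among the excluded is r.

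- Rate among those remaining: p = (0.45 - f × r) / (1 - f)
- Number remaining: n = 365 × (1 - f)
- Standard error: SE = sqrt(p1(1 - p1)/n1 + p2(1 - p2)/n2)
- Rejection probability: normal approximation with mean z = (p1 - p2)/SE and critical value 1.96

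Worked case, one arm only, f = 0.10, r = 0.15: p1 = (0.45 - 0.015)/0.90 = 0.4833, a shift of 3.33 points. With n1 = 328.5 and n2 = 365, SE = 0.0379, z = 0.88 and rejection is 14.2%.

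| Excluded, arm 1 vs arm 2 | Rate among excluded | Shift in difference (points) | Rejection with no true difference |
|---|---|---|---|
| 2% vs 0 | 15% | +0.6 | 5.3% |
| 5% vs 0 | 15% | +1.6 | 7.1% |
| 10% vs 0 | 15% | +3.3 | 14.2% |
| 5% vs 2% | 15% | +1.0 | 5.8% |
| 10% vs 5% | 15% | +1.8 | 7.4% |
| 5% vs 0 | 60% | -0.8 | 5.5% |
| 10% vs 0 | 60% | -1.7 | 7.3% |
| equal, same prognosis | any | 0 | 5.0% |

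A binomial simulation of 400,000 trials with a pooled z test gave 7.2% and 14.3% for the second and third rows, in line with the approximation.

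**The case against.** **The statistical section governs.** Section 12.3 fixes the primary population and promises a detailed analysis plan before data-lock. A statistician following it would keep these women, so harm arises only if a sentence in the enrolment section overrides it. That makes the intended answer fairly clear, but the contradiction remains. Section 7.2 does not leave the matter open for the analysis plan; it states a rule that Section 12.3 forbids. Moreover, the interim look at efficacy and futility after 366 women (Section 12.3.6) may come before a plan promised only by data-lock.

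**A per-protocol reading is possible.** Section 12.3 does not define the per-protocol set, Section 7.2 is the only place that specifies events counted as violations, and However may only contrast a crossover with a violation. This is the weaker reading of an unqualified exclusion that follows an intention-to-treat statement.

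**The sample size seems to expect violators to be lost.** Section 12.1 includes protocol violation in its 10% allowance, which sits closer to Section 7.2 than to Section 12.3. That stands, and it adds to the ambiguity. It also gives a scale: removing 10% of one arm means about 37 women, half of the whole allowance of 73, so that case is an extreme one.

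**The numbers rest on assumption.** The 15% and 60% rates have no source in the protocol, and every case but the most extreme gives at most 7.4% rejection. This stands; the conclusion does not depend on the figures.

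**Intention-to-treat is not always conservative.** Section 12.1 mentions a 5% margin, and under that framing retaining switchers can pull the arms together. This is a reason to keep the per-protocol analysis as a companion, not to leave the primary population contradictory. The primary test in Section 12.3.2 is a test of difference.

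**Conclusion.** The concern holds. The protocol states two incompatible populations for its primary outcome, and the one in Section 7.2 removes women on the basis of post-randomization wishes in an open-label trial. This should be corrected because the primary analysis set needs a single definition; that does not depend on how often the triggers occur.

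The size of any bias is unknown. Across the assumed cases the difference moves by between -1.7 and +3.3 points and the false-rejection rate lies between 5.0% and 14.2%. The upper end requires 10% exclusion confined to one arm and a 15% rate among those excluded. At low exclusion rates the effect is small, and with equal exclusion and equal prognosis it is nil.

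**What to change.** In Section 7.2, reword the end of the sentence so that these women are *excluded from the per-protocol analysis only*. Add that every randomized woman stays in her assigned arm for the primary intention-to-treat analysis, including the interim analysis; Section 12.3.6 names no population, so saying this closes the gap.

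The change is to wording only. It needs no new patients, data or analysis and does not alter treatment, since Section 12.3 already makes intention-to-treat primary and per-protocol a reference. The cost is a protocol amendment, with ethics approval before implementation (Section 1) and DSMB review of the revision (Section 12.3.5). It should be settled before data-lock and, if the interim analysis has not yet taken place, before that, so that the population is not chosen with results in view.

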## **2. PROTOCOL SUMMARY**

### **2.1. Summary**

One of the barriers in patients with diminished ovarian reserve (DOR) is the significantly reduced number of oocytes resulting in fewer oocytes collected and embryos formed. Many ovarian stimulation strategies have been proposed to improve oocyte or embryo quantity which is oocyte accumulation could be a potential option with a comparable success rate and reasonable cost. Dydrogesterone-primed ovarian stimulation (DPOS) protocol effectively blocks the Luteinizing hormone (LH) surge in IVF. It favors segment ART cycles such as FET, oocyte donor, fertility preservation, and oocyte accumulation set. The protocol is more user-friendly and cheaper than the GnRH antagonist regimen regarding LH suppression during ovarian stimulation. Initial evidence suggests that oocyte quantity and quality are comparable with other ovarian stimulation regimens. However, data related to the PPOS protocol has not been well documented. There has not been an RCT with a large sample size and well-designed to provide more substantial evidence. A randomized trial to compare the effectiveness of PPOS and GnRH antagonist protocol in IVF is urgently needed.

The randomized, open-label, multi-center trial will be conducted at IVFTA HCM – Tam Anh TP. Ho Chi Minh General Hospital and IVFTA HN – Tam Anh General Hospital, Vietnam. Patients will be randomized, using a computer-generated randomization list in a 1:1 ratio, to either the DPOS group or the GnRH antagonist group after assessing eligibility and signing informed consent. Randomization will be centrally controlled by a data scientist without involvement in any treatment procedure. After randomization, the patients will be administered human Menopausal Gonadotrophin (HMG) 225 IU/day (IU/d) via intramuscular injection on the 2nd - 4th menstrual day. In the intervention arm, women will receive oral Dydrogesterone 10mg (Duphaston 10mg) t.i.d daily from the first day of ovarian stimulation until final oocyte maturation. In the control arm, GnRH antagonist (Ganirelix 0.25mg) subcutaneously once daily from day 5 of ovarian stimulation will be administered till the day of final oocyte maturation. Oocyte cryopreservation will be applied to collect at least  $7 \pm 1$  oocytes. In the last ovarian

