## 5. STUDY DESIGN

This open-label, randomized, controlled, multi-center clinical trial compares the efficacy and safety of the oral Dydrogesterone primed ovarian stimulation versus fixed gonadotropin-releasing hormone antagonist protocol for accumulating oocytes in patients with low ovarian reserve.

- Study Type: Interventional (Clinical Trial)
- Estimated Enrollment: 730 participants (365 per arm)
- Allocation: Randomized
- Intervention Model: Parallel Assignment
- Masking: Open-label
- Primary Purpose: Treatment
- Official Title: Dydrogesterone primed ovarian stimulation versus fixed gonadotropin-releasing hormone antagonist protocol for accumulation of oocyte in patients with low ovarian reserve: A randomized controlled trial

The Study will be conducted according to the following scheme:

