'morphologically surviving' if there is no dark/degenerated or contracted ooplasm and no cracked zona pellucida. Oocytes with an abnormal oolemma or ooplasm at the time of ICSI should not be excluded (40) Semen samples will be obtained by masturbation after 3–5 days of ejaculatory abstinence. After the samples are liquefied at room temperature, a semen analysis will follow the WHO (2021) guidelines (41). The density gradient procedure will use the Isolate (Irvine Scientific., USA) discontinuous density gradient. Briefly, one aliquot of liquefied semen will be loaded onto 40%, and 80% gradients (each 1.0 ml) with the 80% fraction at the bottom of a 15 ml tube and then will be centrifuged at 300 g for 10 min at room temperature. After centrifugation, the sperm pellet will be washed twice in 3 ml of pre-warmed MHMC [Irvine Scientific., USA] and centrifuged for 5 min at 300 g. The supernatant will be discarded, and the final pellet will be resuspended in a pre-warmed MHMC medium.

Intracytoplasmic sperm injection (ICSI) is performed at 40 hours post-hCG for both the fresh and frozen oocytes and continues to culture in the CXCM medium (Irvine Scientific., USA) (37oC, CO2 6%, O2 5%). Once injected, oocytes were placed in the individual wells. Wells will be filled with 20ul of CXCM medium (Irvine, USA) (37oC, CO2 6%, O2 5%). Fertilization check at 17±1 hours post-ICSI and only normally fertilized zygotes show two pronuclei (2PN) are continued to culture to day 3. The morphology of culture embryos will be assessed at 68±1 hours, 116±2 hours, and 140 ± 2 hours after injection. The evaluated parameters include cell number, symmetry, and percentage of fragmentation for cleavage day 3. Cleavage day 3 embryos with greater than 6 blastomeres will be considered day 3 embryos. All embryos are continued to culture until day 5.

On day 5, the quality of blastocysts will depend on the expansion of the blastocoele cavity and the integrity of both the inner cell mass and trophectoderm cells. Embryos are categorized into four grades (Grade 1: AA, AB, BA, Grade 2: BB, Grade 3: BC, CB, and Grade 4: others). The highest-graded blastocysts with a blastocoel expansion greater than 3 (42) are vitrified (CRYOTEC® Method). The slow-growing embryos (the blastocoel expansion lesser than 3, cleaved embryos) continue to culture to day 6.

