#### *7.3.5. Endometrium preparation and embryo transfer*

At **Visit 9**, all patients undergoing FET will receive oral estradiol valerate (Valiera®; Laboratories Recalcine) 6 mg/day from the 2nd to 4th day of menses for 6 days. The endometrial thickness will be monitored from day six onwards. From day 8-9 of menses, the estradiol dose could be adjusted to 12mg/day according to the development of the

endometrium. Progesterone will be started when endometrial thickness reaches 8 mm or more. Patients will receive micronized Progesterone (Cyclogest® 400mg; Actavis) at the dose of 400mg twice daily (morning and evening) plus dydrogesterone (Duphaston 10mg) at the dose of 10mg twice daily (morning and evening). Estradiol valerate will be decreased to 4 - 8mg/day when starting Progesterone. A single embryo will be thawed on the day of embryo transfer after six or seven days of Progesterone, depending on day-5 or day-6 embryo. After thawing, surviving embryos will be transferred into the uterus under ultrasound guidance. Estradiol and Progesterone will be continued until the day of the pregnancy test. If the pregnancy test is positive, the patients will continue to use 800 mg micronized Progesterone or 800 mg micronized Progesterone plus 20 mg dydrogesterone until 7 weeks of gestation. The blastocyst will be thawed on embryo transferring day (**Visit 10**) according to the CRYOTEC® Method. After warming, the survival blastocyst is evaluated. Blastocyst cryo-survival be defined as at least 75% of cells perceived to be intact after thawing (40). After thawing, the embryo will be cultured in a CXCM medium (37oC, CO2 6%, O2 5%). The embryo will be transferred to the uterus two hours later under ultrasound.

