## 8. OUTCOME MEASUREMENTS

The primary endpoint is ongoing pregnancy after the first embryo transfer. Ongoing pregnancy is defined as pregnancy with a detectable heart rate at 12 weeks' gestation or beyond after the completion of the first transfer. Cycles in which no blastocyst is available for transfer will be considered failures. Several fertility outcomes, characteristics, and outcomes of the ovarian stimulation, patient safety, drop-out rate, and quality of life during oocyte accumulation will be assessed as secondary endpoints. Full details and definitions are provided in Table 2.

**Table 2.** Secondary endpoints and their definition

Secondary endpoints	Definition
LH, Estradiol and progesterone profile	LH, Estradiol, and progesterone level are measured on day 1, day 5, and day 8 of ovarian stimulation, final oocyte maturation day, and 12 hours after the final oocyte maturation injection
Rate of premature LH surge	Premature LH surge (PLS) is increased serum LH more than twice the baseline or more than 15 mIU/ml

	The rate of Premature LH surge is defined as number of PLS appearances per number of ovarian stimulation cycles
Duration of ovarian stimulation	Number of ovarian stimulation days (from the first day of FSH injection to final oocyte maturation injection day)
The total dose of FSH	A number of international units of HMG are administrated during ovarian stimulation
Number of Cumulus-oocyte complex (COCs)	Number of Cumulus-oocyte complexes after oocyte retrieval
Number of MII oocyte	Number of MII oocytes after denuding
Number of survival oocyte	Number of survival oocytes after thawing
Fertilization rate per oocyte inseminated/injected	Fertilisation is defined as the appearance of two PN at 17±1 hour per inseminated/injected
Embryo-cleavage rates	Number of embryos on Day 3 after ICSI day
Blastocyst rate	Numbers of embryos on Day 5 and Day 6 after ICSI
Number of survival blastocyst	Number of survival embryos on Day 5 and Day 6 after thawing
Top-quality blastocyst rate	Numbers of embryos on Day 5 and Day 6 with good quality after ICSI
Positive pregnancy test	A positive pregnancy test is defined as a serum hCG level greater than 25 mIU/mL 11 days after the first transfer
Implantation rate	Implantation rate is defined as the number of gestational sacs per number of embryos transferred 3 weeks after the first transfer
Biochemical pregnancy	Biochemical pregnancy is defined as a pregnancy diagnosed only by the detection of beta hCG in serum or urine

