### **12.2. Randomization**

After signed informed consent, patients will be randomly assigned in a 1:1 ratio to receive one protocol: Antagonist or DPOS. Randomization will be centrally controlled by a data scientist, who is not involved in any treatment procedure. When there is an eligible participant to be enrolled in the Study, clinicians from the specific site will enter the study data management center to get the allocation of patients according to a computer-generated randomization list in a 1:1 ratio, with a variable block size of 2, 4, 6 or 8. Apart from randomization, patients will be followed up and treated according to the protocol at each center.

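### The protocol declares the trial open-label without exception and nowhere masks the embryologists, although their visual grading and freezing calls can reach the primary endpoint

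*Protocol*

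**What the plan says.** Section 2.1 opens with "The randomized, open-label, multi-center trial will be conducted", and the design list in section 5 has "Masking: Open-label". Neither excepts any party. Section 7.2 attributes the open label to the type of intervention and then says who it concerns: "this Study will be label-opened to clinicians who perform ovarian stimulation, oocyte retrieval, and embryo transfer". Embryologists are not mentioned there, either as knowing the arm or as kept from it. The one role set apart from treatment is in section 12.2: "Randomization will be centrally controlled by a data scientist, who is not involved in any treatment procedure". That protects the allocation sequence; it does not mask outcome assessment.

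Sections 7.3.2 to 7.3.4 describe a single laboratory process with no step that depends on the arm. Embryologists judge oocyte maturity and post-thaw survival, grade blastocysts and decide which qualify for freezing. Under section 7.3.5, blastocyst survival means "at least 75% of cells perceived to be intact after thawing".

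Section 8 defines ongoing pregnancy as "pregnancy with a detectable heart rate at 12 weeks' gestation or beyond after the completion of the first transfer" and adds: "Cycles in which no blastocyst is available for transfer will be considered failures". Table 2 lists MII oocytes, surviving oocytes, blastocysts, top-quality blastocysts and surviving blastocysts as secondary endpoints.

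**The concern.** The reason given for an open label does not extend to the laboratory. Nothing an embryologist does differs by arm, so this group could be masked without touching treatment. Yet the only general statement on masking covers everyone, and no sentence takes the laboratory out of it.

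The 12-week heart rate leaves little room for judgement. Reaching it depends on having a blastocyst to transfer, and that depends on what an embryologist sees down the microscope. If knowledge of the arm tilts borderline calls, the laboratory endpoints are exposed directly and the primary endpoint through the no-blastocyst rule. The direction cannot be predicted, so the tilt could create a difference or hide one. Masking is a matter of conduct: an analysis plan written later cannot restore it for embryos that have already been graded.

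**Working it through.** **Who is covered.** Sections 2.1 and 5: open-label, nobody excepted. Section 7.2: the reason and the list of people cover stimulation, retrieval and transfer only. Sections 7.3.2 to 7.3.4: same laboratory handling in both arms. Set side by side, section 5 implies that the laboratory is unmasked, while section 7.2 can be read as confining the open label to clinicians. The text does not settle which is meant.

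**How far written criteria bind.** Section 7.3.3 vitrifies on day 5 "The highest-graded blastocysts with a blastocoel expansion greater than 3" and sends embryos below 3 on to day 6, where they are assessed in the same way. Section 7.3.4 accepts expansion of 3 and above. A blastocyst at exactly 3 is therefore frozen under 7.3.4 but falls under neither branch of 7.3.3. For a woman with no other blastocyst, that call decides whether she has an embryo at all.

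**Size, as illustration.** The plan gives no figure for this bias, so there is none to reproduce.

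Inputs:
- Control ongoing pregnancy rate 45.0%, 365 women per arm, margin 5.0 points (section 12.1).
- No-transfer share b: 9.1% (transfer cancellation in the accumulation group of a cited study) or 17.0% (cycles with no usable blastocyst in a cited diminished-reserve group), both from section 3.
- Extra share x of women in one arm turned into no-blastocyst failures: 1%, 2% or 3%. This is my assumption; the documents give no value.

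Treating 45% as a rate per woman, the average chance per transfer is 0.45/(1 - b):
- b = 9.1%: 0.45/0.909 = 0.495
- b = 17.0%: 0.45/0.83 = 0.542

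Shift in the arm's rate = x × 0.45/(1 - b):

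| x | Women of 365 | b = 9.1% | b = 17.0% | Half the chance |
|---|---|---|---|---|
| 1% | about 4 | 0.50 | 0.54 | 0.25-0.27 |
| 2% | about 7 | 0.99 | 1.08 | 0.50-0.54 |
| 3% | about 11 | 1.49 | 1.63 | 0.74-0.81 |

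Shifts are in percentage points. The last column applies if a borderline embryo has half the average chance. If 45% is already a rate per transfer, the shift is x × 0.45, that is 0.45 to 1.35 points.

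**Effect on the test.** With no true difference, 365 per arm and a normal approximation, let s be the shift and SE = √[(0.45 × 0.55 + (0.45 - s)(0.55 + s))/365]. The two-sided rejection rate is 1 - Φ(1.96 - s/SE) + Φ(-1.96 - s/SE). For s = 0.015: SE = 0.0368, s/SE = 0.408, and the rate is 0.060 + 0.009 = 6.9%. For s = 0.005 and 0.010 it is 5.2% and 5.9%, against a nominal 5%.

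**The case against.** The strongest reply is that no sentence says embryologists know the arm. Section 7.2 does not list them, clinicians rather than the laboratory obtain the allocation, and nothing says worksheets carry it. That stands. A reader might infer from section 5 that embryologists are unmasked; the documents support only that their masking is not stated.

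The calls are also bounded. Maturity rests on the first polar body, fertilization on two pronuclei at a fixed time, and blastocysts on named grades. Abnormal-looking oocytes are not to be dropped at ICSI, and the couple has a say on freezing at Visit 8. This shrinks the room for bias. It does not close it, because the freezing threshold itself is stated in two ways.

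Four further inferences are tempting and are not supported:
- That only clinicians need to know the arm. Patients take either tablets or injections and cannot be masked.
- That a survival call at thaw by itself makes a woman a failure. Section 8 does not say whether a thaw loss counts as no blastocyst available, and such a loss matters only if no other blastocyst can be used.
- That these women often have a single borderline blastocyst. The protocol cites a median of 2 usable blastocysts (0-3) in a diminished-reserve group and plans to accumulate oocytes over several cycles; it says nothing about how often there is only one, or a borderline one.
- That embryo-count endpoints shift by the same points as the share of women with any blastocyst. The units differ.

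Finally, x is a bare assumption. A shift of 1-3% of women equals 11-33% of a 9.1% no-transfer share (1/9.1 to 3/9.1), or 6-18% of a 17.0% share, and embryologists have no stated preference between arms. The upper figures should be read with that in mind.

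**Conclusion.** The point holds as a gap in the design that is cheap to close. The open label has no exception, its stated reason does not reach the laboratory, and visual laboratory calls feed secondary endpoints and, through the no-blastocyst rule, the primary one. The documents do not show that bias has occurred or how large it would be. Under the assumption above, the primary rate in one arm moves by about 0.5-1.6 points, or about 0.25-0.8 if marginal embryos do half as well. At most that is roughly a third of the 5-point margin (1.63/5 = 33%). This is a modest effect on the primary comparison, and the case for acting rests mainly on the low cost.

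**What to change.** In sections 5 and 7.2, state: open-label to patients and treating clinicians; embryologists who assess, grade, freeze and thaw oocytes and embryos are masked to arm.

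To carry this out:
- Leave the arm and the stimulation drugs off laboratory worksheets.
- Give embryologists no access to the allocation.
- Keep the laboratory's usual patient identification unchanged; the study code in section 13.3 may be added.
- Reconcile the freezing thresholds in sections 7.3.3 and 7.3.4. Which one applies is for the investigators to settle.

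The cost is a protocol amendment with ethics approval and a change to laboratory paperwork. Existing staff should suffice, though the protocol does not describe the request forms, so each site should confirm this. Masking may sometimes be broken through the clinical record, and it cannot cover embryos already graded. By 22 August 2024, 272 of 730 women had been recruited (summary of changes), which left 458, or 63%, still to come at that date.
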